12.2. LABORATORY RESULTS

In the context of this study the difference between potentially clinically important (PCI) and PCS results are defined as follows:

- A PCS result is defined as an abnormal laboratory assay result marked as clinically significant in the Investigator's opinion.
- A PCI result is defined as a laboratory assay result that meets criteria tested against as used by the local laboratory for identifying as PCI.

[figure not shown]
The following subject safety laboratory result items are planned to be listed using the SAS for both protocol parts:

- Chemistry
- Hematology
- Urinalysis
- Drug and Alcohol Screening
- Abnormal results
- PCS results
- PCI results

The following local laboratory result items are planned for table presentation, by treatment groups for each applicable visit using the SAS:

- Chemistry:
 - CFB with descriptive statistics
 - Shift from Baseline with summary statistics
- Hematology:
 - CFB with descriptive statistics
 - Shift from Baseline with summary statistics
- Urinalysis:
 - CFB with descriptive statistics for numeric results
 - Qualitative summary of Urinalysis
- PCI laboratory results as tested against local laboratory criteria set (see Appendix IV: Potentially Clinically Important Values for list of criteria)
- Marked abnormalities, including the following criteria:
 - Alanine aminotransferase (ALT) $> 1.5 \times$ upper limit of normal (ULN)
 - Bilirubin $> 1.5 \times$ ULN (where if fractioned, direct bilirubin $\geq 35\%$)
 - ALT or aspartate aminotransferase (AST) $> 3 \times$ ULN and total bilirubin (TBL) $> 2 \times$ ULN and alkaline phosphatase (ALP) $> 1.5 \times$ ULN (Hy's law)

A list of local laboratory assays planned to be performed can be found in Appendix III: Appendix III: Summary of Laboratory Assays Performed. The planned timings of laboratory sample collection are given in Appendix I: Schedule of Assessments and Procedures.

The following ECG listings will be presented for both protocol parts using the SAS:

- Quantitative results containing all the measurements listed in Table 3.
- Potentially clinically significant results.

The following ECG summary tables are planned, by treatment groups using the SAS:

- CFB with descriptive statistics on all the measurements listed in Table 3.
- Categorical Outliers and marked abnormalities, including the following criteria:

For marked abnormalities:

- QTcB > 450 (msec) for male subjects.
- QTcB > 470 (msec) for female subjects.
- Increase in QTcB from baseline ≥ 60 (msec).
- Increase in heart rate CFB% $\geq 30\%$ AND observed heart rate > 90 (bpm).

For categorical outliers:

- QTcB > 500 (msec).
- Increase in QTcB from baseline ≥ 30 (msec) and < 60 (msec).
- Increase in QTcB from baseline ≥ 60 (msec).
- Time-matched, placebo-adjusted QTcB CFB for all post-dose timepoints ≤ 24 hours.

The following figures are planned for presentation ECG parameter QTcB for both parts of study by treatment groups using the SAS:

- Mean observed values after study drug infusion on dosing days (by dose group)
- Mean observed values over time (excluding post-dose assessments on dosing days)
- Mean CFB after study drug infusion on dosing days (by dose group)

-
- Mean CFB over time (excluding post-dose assessments on dosing days)
 - Placebo-corrected mean CFB in QTcB with 90% CI whiskers across post-dose timepoints up to 24 hours (by dose group)

A time-matched analysis of change in QTcB will be graphically explored. The mean CFB in QTcB versus placebo will be plotted at the different timepoints \leq 24 hours post-dose, along with 90% 2-sided CI. The upper limit of the 90% CI should be below the 10 (msec) bound as provided by the International Conference on Harmonization (ICH) E14 guideline to be deemed as having no QTc prolongation effect. Due to the small number of subjects planned per cohort, subjects from the different cohorts will be pooled into active treatment and placebo. If any upper limits are observed above the 10 (msec) mark from the pooled plot, further exploration by cohort may be explored. The estimates and 90% CI will be obtained through an analysis of covariance (ANCOVA), using baseline QTcB as covariate and treatment (pooled active and placebo) as effect.

The following example SAS® code can be utilized and modified as needed:

```
Proc GLM Data = <Dataset>;
  By <Tmpt>;
  Class <TRT>;
  Model <CFB> = <TRT> <BaseVal> / solution;
  LSmeans <TRT> / diff cl Alpha = 0.1 pdiff;
  ods output LSMeanDiffCL = <estmt>;
  Run;
Quit;
```

Where <Dataset> is the input dataset, <Tmpt> is the timepoint, <TRT> is the treatment group, <BaseVal> is the baseline value and <estmt> is the output set containing the estimate and corresponding 90% CI.

The data for these presentations will be obtained from the following eCRFs:

- 12-Lead Electrocardiogram Details.
- Vital Signs (for heart rate).

Table 3 below gives the ECG measurements to be assessed.

Table 3. ECG Measurements

Measurement
QT interval (msec)
QT, corrected with Bazett's formula (QTcB) interval (msec)
QRS interval (msec)
PR interval (msec)
Heart Rate (HR) (bpm)

The planned timings of these ECG are given in Appendix I: Schedule of Assessments and Procedures.

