10.3 Appendix 3: Liver Safety: Suggested Actions and Follow-up Assessments

Phase 1 liver chemistry stopping criteria define liver injury, evaluate liver event etiology, and are considered in dose escalation decisions.

Table 9. Phase 1 Liver Chemistry Stopping Criteria and Follow-up Assessments

Liver Chemistry Stopping Criteria			
ALT-absolute	Alanine aminotransferase (ALT) \geq 3 × upper limit of normal (ULN) If ALT \geq 3 × ULN AND bilirubin \geq 2 × ULN (> 35% direct bilirubin) or international normalized ratio (INR) > 1.5, report as a serious adverse event (SAE) ^{a,b}		
	See additional actions and follow-up assessments below		
	Required Actions and Follow-up Assessments		
Actions		Follow-Up Assessments	
 Report the ev 24 hours Complete the (CRF), and co collection too criteria for an Perform liver assessments Monitor the pabnormalities 	discontinue study drug ent to the sponsor within liver event case report form complete an SAE data il if the event also met the SAE ^b function follow-up catient until liver function test resolve, stabilize, or return ee MONITORING)	 Viral hepatitis serology^c Obtain INR and recheck with each liver chemistry assessment until the transaminases values show downward trend Serum creatine phosphokinase (CPK) and lactate dehydrogenase (LDH) Fractionate bilirubin, if total bilirubin ≥ 2 × ULN Complete blood count with differential to assess eosinophilia Record the appearance or worsening of 	
 MONITORING: If ALT ≥ 3 × ULN AND bilirubin ≥ 2 × ULN or INR > 1.5 Repeat liver function tests (include ALT, aspartate transaminase [AST], alkaline phosphatase, bilirubin and INR) and perform liver function follow-up assessments within 24 hours. Monitor patient twice weekly until liver function test abnormalities resolve, stabilize, or return to baseline. 		 Record the appearance of worsening of clinical symptoms of liver injury, or hypersensitivity, on the AE CRF Record use of concomitant medications (including acetaminophen, herbal remedies, and other over-the-counter medications) on the concomitant medications CRF Record alcohol use on the liver event alcohol intake CRF If ALT ≥ 3 × ULN AND bilirubin ≥ 2 × ULN or INR > 1.5: 	

Protocol TB006AD2102

Protocol Date and Version: 15 Oct 2021; v 3.0

 A specialist or hepatology consultation is recommended.

If ALT \geq 3 × ULN AND bilirubin < 2 × ULN and INR \leq 1.5:

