- Repeat liver function tests (include ALT, AST, alkaline phosphatase, bilirubin and INR) and perform liver function follow-up assessments within 24 to 72 hours
- Monitor patients weekly until liver function abnormalities resolve, stabilize, or return to baseline
- Anti-nuclear antibody, anti-smooth muscle antibody, Type 1 anti-liver kidney microsomal antibodies, and quantitative total immunoglobulin G (IgG) or gamma globulins
- Serum acetaminophen adduct high performance liquid chromatography assay (quantifies potential acetaminophen contribution to liver injury in patients with definite or likely acetaminophen use in the preceding week [James et al, 2009])
- Liver imaging (ultrasound, magnetic resonance, or computerized tomography) and/or liver biopsy to evaluate liver disease; complete liver imaging and/or liver biopsy CRFs
- a Serum bilirubin fractionation should be performed if testing is available. If serum bilirubin fractionation is not immediately available, discontinue study drug if $ALT \ge 3 \times ULN$ and bilirubin $\ge 2 \times ULN$. Additionally, if serum bilirubin fractionation testing is unavailable, **record the absence/presence of detectable urinary bilirubin on dipstick** which is indicative of direct bilirubin elevations suggesting liver injury.
- b All events of ALT ≥ 3 × ULN and bilirubin ≥ 2 × ULN (> 35% direct bilirubin) or ALT ≥ 3 × ULN and INR > 1.5 may indicate severe liver injury (possible 'Hy's Law') and must be reported as an SAE (excluding studies of hepatic impairment or cirrhosis). The INR stated threshold value will not apply to patients receiving anticoagulants.
- c Includes: Hepatitis A immunoglobulin M (IgM) antibody; hepatitis B surface antigen and hepatitis B core antibody; hepatitis C RNA; cytomegalovirus IgM antibody; Epstein-Barr viral capsid antigen IgM antibody (or if unavailable, heterophile antibody or monospot testing); and hepatitis E IgM antibody.

Protocol TB006AD2102

Protocol Date and Version: 15 Oct 2021; v 3.0

A patient who met liver chemistry stopping criteria cannot restart study drug unless all of the following conditions are met:

• TrueBinding Inc. approval is granted (as described below)

- Institutional Review Board/Independent Ethics Committee (IRB/IEC) approval is obtained
- Separate ICF for study drug restart/rechallenge is signed by the patient

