8. CHANGES IN CONDUCT OR PLANNED ANALYSES FROM THE PROTOCOL

The following analyses described in this SAP are not mentioned in the study protocol:

- Assessment of dose proportionality (see Section 10.5: Pharmacokinetics).

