9.7. VISIT WINDOWS/UNSCHEDULED VISITS

No mapping/renaming of visits (unscheduled or otherwise) will be done for this study. That is, only regular scheduled visit data will be used for summarization in tables. However, all collected data will be listed.

Unscheduled visits will be considered eligible for Baseline values. Unscheduled visit results will also be considered eligible for testing of potentially clinically significant (PCS) values (laboratory, Electrocardiogram (ECG) and vital signs).

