2. PURPOSE

The Statistical Analysis Plan (SAP) version 2.0 dated 11 April 2022 need to clarify the definition of Efficacy Analysis Set-Part 2 (EAS2). The EAS2 is defined in SAP as:

The Part 2 – Efficacy Analysis Set (EAS2) includes all subjects who received assigned dose of TB006 in Part 2 and the subjects enrolled at the same TB006 dose level in Part 1, as well as all placebo patients will be included and have at least one post-dose evaluable PD assessment across subject.

Here “PD assessment” can be mistaken to refer to plasma or imaging biomarkers and hence the definition for EAS2 is clarified in addendum SAP to replace text “PD” with text “efficacy”. The updated definition is as under:

The Part 2 – Efficacy Analysis Set (EAS2) includes all subjects who received assigned dose of TB006 in Part 2 and the subjects enrolled at the same TB006 dose level in Part 1, as well as all placebo patients will be included and have at least one post-dose evaluable **efficacy** assessment across subject.

3. DESCRIPTIONS OF CHANGES IN STUDY CONDUCT AND ANALYSIS PLANNED IN PROTOCOL AND STATISTICAL ANALYSIS PLAN

This change will only impact the analysis population definition in SAP version 2.0 dated 11 April 2022, Section 7.1.5.

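### The SAP's Hy's law row requires ALP > 1.5 × ULN, which the protocol's definition does not, so it cannot count any protocol-defined case with ALP at or below that level

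*SAP*

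**What the plan says.** SAP Section 12.2 lists three liver criteria under marked abnormalities. Two concern a single analyte: ALT > 1.5 × ULN, and bilirubin > 1.5 × ULN with a direct-fraction qualifier. The third reads "ALT or aspartate aminotransferase (AST) $> 3 \times$ ULN and total bilirubin (TBL) $> 2 \times$ ULN" "and alkaline phosphatase (ALP) $> 1.5 \times$ ULN (Hy's law".

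Protocol Section 10.3 (Appendix 3) defines the same concept differently. Table 9, footnote b covers "All events of ALT ≥ 3 × ULN and bilirubin ≥ 2 × ULN (> 35% direct bilirubin" and continues "or ALT ≥ 3 × ULN and INR > 1.5 may indicate severe liver injury". It names such events possible Hy's Law and makes SAE reporting mandatory. The body of Table 9 gives the same INR alternative: "or international normalized ratio (INR) > 1.5, report as a serious adverse event (SAE". ALP appears in that appendix only among the liver tests to be repeated during monitoring.

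SAP Section 8, on changes from the protocol, has one entry: "Assessment of dose proportionality (see Section 10.5: Pharmacokinetics". The SAP addendum rewords the EAS2 definition and says of its own scope: "This change will only impact the analysis population definition in SAP version 2.0".

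**The concern.** The two documents use one label for two different sets of patients, and the SAP's set carries a condition found nowhere in the protocol's definition. A reader of the safety tables will take the row as the count of Hy's law cases. Safety is a primary endpoint in Part 1 and a secondary one in Part 2, and Appendix 3 says its liver criteria feed into dose-escalation decisions. A table showing none, next to an SAE narrative of possible Hy's Law, would be contradictory and could be read as reassurance.

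No other listed laboratory criterion would supply the count. This is the only one of the three that combines a transaminase with bilirubin, and the limits in SAP Appendix IV are set one analyte at a time.

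**Working it through.** The plan gives no figure to reproduce, so the check compares the two rules. All values except the direct-bilirubin percentage and INR are multiples of ULN.

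- **Protocol** (Table 9, footnote b): ALT ≥ 3 AND [(bilirubin ≥ 2 AND direct > 35%) OR INR > 1.5].
- **SAP row** (Section 12.2): (ALT > 3 OR AST > 3) AND bilirubin > 2 AND ALP > 1.5.

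If ALP ≤ 1.5, the last SAP term is false and so is the whole rule, whatever the other values. The omission is therefore a matter of logic and needs no assumed frequency.

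The following profiles were chosen to show how the rules part. INR is taken as ≤ 1.5 unless stated.

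| Profile | Protocol | SAP row | SAP row without ALP term |
|---|---|---|---|
| A: ALT 10, bilirubin 3, direct 50%, ALP 1.0 | yes | no | yes |
| B: as A, ALP 1.5 | yes | no | yes |
| C: as A, ALP 1.6 | yes | yes | yes |
| D: ALT 10, bilirubin 1, INR 2.0, ALP 1.0 | yes | no | no |
| E: ALT 3.0, bilirubin 2.0, direct 50%, ALP 2.0 | yes | no | no |

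The SAP row flags 1 of these 5 protocol-defined profiles. Deleting the ALP term gives 3 of 5. D then still needs the INR route, and E needs the ≥ cut-offs.

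In the other direction, once the ALP term is gone the row would also flag two profiles that the protocol does not define as cases: F (AST 10, ALT 1, bilirubin 3) and G (ALT 10, bilirubin 3, direct 20%, ALP 1.0). Deleting ALP alone therefore does not align the definitions.

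A wider logic check used 2,304 combinations: ALT 1, 2, 3, 3.1, 5, 10; AST 1, 3, 4, 8; bilirubin 1, 2, 2.1, 4; direct 20%, 50%; INR 1, 2; ALP 0.8, 1.0, 1.5, 1.6, 2, 3 (6 × 4 × 4 × 2 × 2 × 6 = 2,304). The protocol rule is met in 1,056.

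- ALP ≤ 1.5: 528 cases, of which the SAP row captures 0. Without the ALP term it would capture 252. The remaining 276 (528 − 252) have bilirubin ≤ 2 (INR-only cases or exactly 2), or ALT exactly 3 without AST > 3.
- ALP > 1.5: 528 cases, of which the SAP row captures 252.
- Bilirubin route with values strictly above the cut-offs (ALT > 3, bilirubin > 2, direct > 35%): 288 cases. The SAP row captures 144, and all 288 without the ALP term.

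These counts depend on the chosen grid and are not estimates of frequency. The zero does not depend on it.

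**The case against.** The strongest reply is that no planned analysis is altered. Table 9 is a stopping and reporting rule; the protocol's statistical section asks for no Hy's law table, and SAP Section 8 is worded as a list of analyses the protocol lacks. Patient handling is unaffected, because every protocol-defined case is reported to the sponsor within 24 hours and as an SAE whatever the SAP says. The case would then appear in the SAE displays, the ALT > 1.5 × ULN row, usually the bilirubin row, and the chemistry and PCI listings. Only about 140 patients are planned (24 + 116), and raised ALT or bilirubin is largely excluded at entry. All this stands. It limits the damage to one descriptive table, but it does not make the row's count right under the label it carries.

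A second reply is that the list of marked abnormalities is introduced as non-exhaustive. That would allow another row to be added; it does not correct this one.

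A third concerns unscheduled samples. SAP Section 9.7 says "only regular scheduled visit data will be used for summarization in tables", but goes on to make unscheduled results eligible for testing of potentially clinically significant values. Section 12.4 links that term to marked abnormalities for vital signs, whereas Section 12.2 defines it for laboratory results by investigator opinion. Whether follow-up liver samples count for this row is therefore unclear rather than ruled out.

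Finally, the text was extracted from PDF, so the sign before 1.5 should be checked against the source. Neighbouring signs look intact. A different sign would change which cases are lost, but an undeclared ALP condition would remain.

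**Conclusion.** The concern holds. As written, the Hy's law row excludes every case that the protocol calls possible Hy's Law when ALP is ≤ 1.5 × ULN, and the SAP neither declares nor explains this. The conclusion rests only on the wording of the two definitions. The number of patients affected cannot be estimated from the documents and may well be zero.

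Four smaller mismatches sit in the same row: > instead of ≥, no direct-bilirubin qualifier, no INR route, and an AST branch the protocol definition lacks. The other two liver criteria in Section 12.2 follow the thresholds of protocol exclusion criterion 8, so the departure looks more like a slip than a choice. It should be fixed before the safety tables are produced. It does not touch efficacy, the stopping criteria or SAE reporting.

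**What to change.** SAP Section 12.2 and Protocol Table 9, footnote b must be reconciled for tabulation:

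1. Delete the ALP > 1.5 × ULN condition from the Hy's law row and list ALP descriptively for each flagged patient.
2. Use the ≥ cut-offs. Apply the > 35% direct-bilirubin qualifier where bilirubin was fractionated. Add the INR route where an INR was obtained, leaving out patients on anticoagulants as footnote b does.
3. If AST-based cases are wanted, show them in a separately labelled row.
4. State whether unscheduled follow-up samples count for this row. INR is in neither the protocol's scheduled laboratory panel (Table 5) nor the SAP's assay list (Appendix III), so without such samples the INR route would be empty.
5. If the ALP condition is deliberate, declare and justify it in SAP Section 8 and do not label the row Hy's law without explanation.

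The cost is a few lines of SAP wording and a small change to one flag derivation. Bilirubin fractions and ALP are already collected, and INR exists where liver follow-up was triggered. No new data collection is needed, and no stopping or treatment rule changes.

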1.3 Schedule of Activities (SoA)

Table 1. Part	1 - Sche	dule	of A	ctivit	ies													
	-2ª						St	udy I)rug	Adm	inistr	atior	Per:	iod				Notes
	Screening D -28 to D -2	D -2ª	D-1ª	DIa	D2-6 ^a	D8	D9-13ª	D15a	D16-20ª	D22ª	D23-27a	D29a	D30-34ª	D36ª	D64ª	D104a	E/Db	
							Gene	ral a	nd Sa	ifety .	Asses	smei	ıts					
Informed consent	X																	*
Eligibility criteria	x		X								,				9 3			Recheck eligibility before randomization and/or first dose of study drug
Medical history ^c (includes substance usage)	х	Х	х															Medical occurrences that begin before the start of study drug but after obtaining informed consent will be recorded on the Medical History/Current Medical Conditions section of the CRF, not the AE section
Demography	X																	
Physical and neurological examination	x		X											X		X	X	Physical examination will include height (screening only) and weight measurements; see also Section 8.2.1
Randomization			X															

CONFIDENTIAL Page 20 of 101

Protocol TB006AD2102

Protocol Date and Version: 15 Oct 2021; v 3.0

Table 1. Part	1 - Sche	dule	of A	ctivit	ies													
	-2"						St	udy l	Drug	Adm	inisti	ation	ı Per	iod				Notes
	Screening D -28 to D -2	D -2a	D-1ª	D1ª	D2-6ª	BQ	D9-13ª	D15a	D16-20ª	D22ª	D23-27a	D29a	D30-34a	D36 a	D64ª	D104ª	E/D ^b	
Vital signs	X		х	х		X		X		X		X		X	X	X	x	Pre-dose, then 2 and 6 hours after the end of the study drug infusion on D1, D8, D15, D22, D29; otherwise once on the days indicated; see Section 8.2.2 for vital signs assessments
12-lead ECG	х		X	X		x		X		X		X		X	X	X	X	D1, D8, D15, D22, D29: pre-dose, then 2 and 6 hours after end of study drug infusion D-1, D36, D64, D104, E/D: time-matched with D1, D8, D15, D22, D29 pre-dose to the extent possible
AE monitoring				X	X	X	X	X	X	X	X	X	X	X	X	X	X	All AEs and SAEs will be collected from the time of the first study drug administration until D104.
Prior/concomitant medication review	X	X	X	X	X	X	X	X	X	X	X	X	X	X	X	X	X	
C-SSRS	X			X		X		X		X		X		X	X	X	X	

CONFIDENTIAL Page 21 of 101

Protocol TB006AD2102

Protocol Date and Version: 15 Oct 2021; v 3.0

Table 1. Part 1	- Sche	dule	of A	ctivit	ies													
	g -2ª						St	udy l	Drug	Adm	inistr	atior	ı Per	iod				Notes
	Screening D -28 to D -2	D -2ª	D-1ª	D1ª	D2-6ª	D8	D9-13ª	D15a	D16-20ª	D22ª	D23-27a	D29a	D30-34a	D36 a	D64ª	D104ª	E/D _b	

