6.4 Measures to Minimize Bias: Randomization and Blinding

6.4.1 Randomization

All patients will be centrally assigned to randomized study drug using an IWRS. Before the study is initiated, the log in information and directions for the IWRS will be provided to each site.

In Part 1, 8 patients will be enrolled into each dose group; 6 patients in each group will be randomized to active TB006 treatment, and 2 patients to placebo (with 3 dose groups planned, for a total of 18 patients receiving TB006 treatment at different dose levels, and a total of 6 patients receiving placebo). In Part 2, 116 patients will be randomized to active TB006 or placebo (1:1) and will follow the same dosing schedule and procedures (with some exceptions – see SoA) as in Part 1. Randomization in Part 2 will be stratified according to baseline patient severity, with mild AD patients (MMSE 21-24) and moderate-severe AD patients (MMSE \leq 20) in each strata.

On Day 1, patients will be assigned a unique number (randomization number) in ascending numerical order as patients are enrolled. Once a randomization number has been assigned, it must not be re assigned. The randomization number encodes the patient's assignment to either active TB006 treatment or placebo, according to the randomization schedule generated prior to the study. Each patient will receive blinded study drug, labeled with his/her unique randomization number.

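### In Part 1 (18 v 6, 10 post-dose ECG timepoints) the 10 ms QTc rule has low power to clear a harmless drug, so a failure says little; the example code also leaves dosing day and patient out.

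*SAP*

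**What the plan says.** SAP Section 12.3 (Electrocardiogram) introduces the analysis as graphical: "A time-matched analysis of change in QTcB will be graphically explored". The difference from placebo in mean QTcB change is plotted at each timepoint up to 24 hours post-dose, "along with 90% 2-sided CI". The decision wording follows: "The upper limit of the 90% CI should be below the 10 (msec) bound" for the drug "to be deemed as having no QTc prolongation effect". Because cohorts are small, "subjects from the different cohorts will be pooled into active treatment and placebo". The follow-up is optional: "If any upper limits are observed above the 10 (msec) mark from the pooled plot, further exploration by cohort may be explored". Since any single limit above 10 ms opens that step, clearance in effect means that every limit lies below 10 ms.

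The example code is a PROC GLM run by `Tmpt`, with treatment and baseline QTcB in the model. `Tmpt` is defined only as the timepoint. Neither dosing day nor patient appears in the code.

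The Part 1 schedule (Protocol Table 1) sets the ECG times: "D1, D8, D15, D22, D29: pre-dose, then 2 and 6 hours after end of study drug infusion". That is 2 x 5 = 10 post-dose timepoints. Protocol Section 6.4.1 gives the Part 1 sizes: "for a total of 18 patients receiving TB006 treatment at different dose levels, and a total of 6 patients receiving placebo". The QTcB figures are planned for both parts. Part 2 has 58 patients per arm (Protocol Section 6.4.2) and a post-dose ECG on each of five dosing days (Protocol Table 2).

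**The concern.** ECGs are among the Part 1 primary safety endpoints, and this is the only group-level QTc criterion in the SAP with a conclusion attached. It asks ten separate confidence limits, each resting on 6 placebo patients, all to fall below 10 ms. Neither document gives an SD, a power or a false-alarm rate for it. If a harmless drug often fails, a failure cannot be told from noise, and the only stated next step splits the data into cohorts and so loses more precision.

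The code raises a separate matter. If it is run as written with `Tmpt` meaning 2 h or 6 h, each fit holds five records per patient as if they came from five different patients. The interval is then too narrow, and the error goes the other way: a prolonging drug is cleared too often.

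**Working it through.** The plan states no QTc operating characteristic, so there is no figure to reproduce.

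**Inputs.** From the documents: margin 10 ms; two-sided 90% interval (5% one-sided per timepoint); Part 1 18 v 6 with 10 timepoints; Part 2 58 v 58 with 5 timepoints. Assumed, because the documents do not give them: SD of QTcB change 6 to 15 ms, and equal within-patient correlation of 0.3 to 0.8 between timepoints.

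**Step 1. Half-width of one interval.** Half-width = t(0.95, n1+n2-3) x SD x sqrt(1/n1 + 1/n2).
- Part 1, 18 v 6: 1.721 x 0.471 = 0.811 x SD
- One cohort, 6 v 6 (all placebo patients kept): 1.833 x 0.577 = 1.058 x SD
- Part 2, 58 v 58: 1.658 x 0.186 = 0.308 x SD

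**Step 2. Part 1, no drug effect, by day and hour.** The one-timepoint column is from the noncentral t. The last column is from simulation of the ANCOVA at correlation 0.3-0.7.

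| SD (ms) | Half-width (ms) | Passes one timepoint | Fails at one or more of 10 |
|---|---|---|---|
| 6 | 4.9 | 96% | 15-25% |
| 8 | 6.5 | 82% | 48-69% |
| 10 | 8.1 | 66% | 70-89% |
| 12 | 9.7 | 53% | 81-97% |
| 15 | 12.2 | 39% | 90-99% |

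As a bound at SD 10: fully correlated timepoints would give 1 - 0.66 = 34% failure, and independent ones 1 - 0.66^10 = 98%. The simulated range lies between. Failure passes 50% at SD 7.0, 7.5, 8.2 and 8.8 ms for correlation 0.3, 0.5, 0.7 and 0.8, hence the summary of about 9 ms or more.

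**Step 3. What pass and fail tell the reader.** At SD 10 and correlation 0.5, the simpler two-sample version passes at all 10 timepoints in 20% of trials (true effect 0), 1.4% (5 ms) and essentially 0% (10 ms). Failure rates are therefore 80%, 98.6% and about 100%. A pass is strong evidence. A failure is the likely result whether or not the drug prolongs QTc.

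**Step 4. By-cohort follow-up.** At SD 10 the 6 v 6 half-width is 10.6 ms, already above the margin. A no-effect drug passes all 10 timepoints 3-20% of the time (correlation 0.3-0.8).

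**Step 5. Part 2, by dosing day.** At SD 10 the half-width is 3.1 ms and a no-effect drug passes all 5 timepoints in over 99% of trials. At SD 15 the half-width is 4.6 ms and the pass rate is about 90%.

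**Step 6. Hour-only reading.** With five records per patient and correlation r, the true variance of a patient's mean is (1 + 4r) times what the model assumes: 2.2, 3.0 and 3.8 for r = 0.3, 0.5 and 0.7. The standard error is too small by the square roots, 1.48, 1.73 and 1.95. A limit meant to sit 1.66 standard errors out then sits only 1.12, 0.96 and 0.85 out. With a true effect of 10 ms, that gives false clearance near 13%, 17% and 20%. Simulation gives 13%, 17% and 21% at one hour, and 7%, 11% and 16% if both hours must pass, against 5%. Part 2 size does not help: 12%, 17% and 20% there.

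**The case against.** The strongest reply has four parts.

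- **Part 2 is large enough.** This stands for the by-day reading, as Step 5 shows. A reader might infer that the whole trial rests on 6 placebo patients; the documents do not support that. But the SAP does not say which part carries the conclusion, and it justifies pooling by small cohorts, which describes Part 1.
- **The rule is conservative.** This stands for the by-day-and-hour reading. A reader might infer that the rule cannot tell a safe drug from a prolonging one. That is too strong: a true 10 ms drug almost never passes, so false clearance is well controlled. The weakness is false alarms.
- **The analysis is exploratory.** This largely stands. It is labelled graphical, failure leads only to optional exploration, and no dose decision cites it. The SAP also tabulates QTcB outliers, Protocol Section 7.2 has a patient-level QTc criterion, and Section 6.2.1 has the safety committee weigh QTc increases. Nowhere is a failure called evidence of prolongation. Yet the SAP does attach a no-prolongation verdict to a pass and leaves a failure unexplained.
- **The SD may be small.** Triplicate ECGs and central reading in Part 1 (Protocol Section 8.2.3) both help. At SD 6 a harmless drug usually passes, so frequent failure is conditional on the SD.

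The hour-only reading is not certain either. The text speaks of time-matched comparisons at different timepoints, and the code is an example that may be modified. On that reading a no-effect drug would pass 93-97% of the time; the fault there is the excess false clearance.

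**Conclusion.** The point holds for Part 1. With 18 v 6 patients and 10 timepoints, the rule has low power to clear a harmless drug if the SD of QTc change is about 9 ms or more: failure in 70-89% of trials at SD 10, against 15-25% at SD 6. These figures rest on assumed SDs and on equal correlation of 0.3-0.7 between timepoints. A Part 1 failure should be read as inconclusive, and going to 6 v 6 makes it more so. Part 2 run by dosing day is sound up to about SD 15.

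The code ambiguity is a second, smaller defect. It affects both parts and errs toward false clearance. The documents do not show that the rule would mislead a dose decision or that it fails in general.

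**What to change.** 1. Define `Tmpt` as dosing day and hour. Keep the by-timepoint ANCOVA as a descriptive plot in Part 1. State that a Part 1 limit above 10 ms is inconclusive, and name the part that supports the QTc conclusion.
2. For Part 1, add one prespecified linear mixed concentration-QTc model, using ECGs with a matched PK sample (pre-dose, 2 h and 6 h on Days 1, 8 and 29). Fixed effects: nominal day/time, TB006 concentration (zero for placebo) and a treatment-specific intercept. Random effect: patient. Apply the 10 ms bound once, to the upper 90% limit of the predicted placebo-corrected change at the geometric mean Cmax of the highest dose, including the treatment intercept.

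At SD 10 and correlation 0.5 (also assuming a 10-day half-life and 30% exposure CV), clearance of a harmless drug rises from about 19% to 70%. A true 10 ms effect is cleared about 4% of the time if it is linear in concentration or constant across doses, and about 8% if it saturates. The treatment intercept must stay: without it, a constant 10 ms effect is cleared about half the time.

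The cost is SAP wording and one model on data already collected. The downside is reliance on approximate linearity, to be checked with residual plots.
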